5.1.2.7 Intraprostatic Injection Procedure

Subjects will be seen as outpatients the day of the adenovirus injection. The injection procedure will be performed in a private treatment room with restricted access. Biosafety Level 2 procedures will be followed throughout.

Adenovirus injections will be performed transrectally under transrectal ultrasound guidance (TRUS) typically using 20 gauge needles. The subject will be placed in the left lateral decubitus position with the legs flexed and the knees brought up toward the chest. The buttocks are placed over the edge of the examining table to allow for the appropriate manipulation of the ultrasound probe. Prior to the adenovirus injection, the subject will receive a local injection of 1% lidocaine into the area surrounding the prostatic capsule. Two needle passes (one medial, one lateral) will be made in the left and right sides of the prostate starting at the base and proceeding toward the apex until all of the adenovirus is delivered.

Used syringes and needles will be disposed of properly. After the procedure, the treatment room will be cleaned with an approved disinfectant.

5.1.2.8 **Toxicity**

Injection procedure- Possible side effects of the injection procedure include infection, gross hematuria and urinary retention. Infection occurs in less than 1% of cases. Antibiotic therapy will be given as prophylaxis prior to and after the adenovirus injection. Gross hematuria following prostate biopsy occurs in less than 1% of cases and is usually self-limited. Injection of the adenovirus into the prostate may cause local swelling that could lead to acute urinary retention. A Foley catheter will be placed, if needed.

Ad5-*yCD/mutTK_{SR39}rep-hIL12* adenovirus- Based on the results of five phase 1/2 trials with similar oncolytic adenoviruses lacking IL-12 (36-44), likely adverse events attributable to the oncolytic adenovirus include transient flu-like symptoms (37 of 79 subjects or 47%) and transaminitis (32 of 79 subjects or 41%). The vast majority (> 94%) of these events were mild (grade 1) to moderate (grade 2). The flu-like symptoms typically resolve within a few days and can be alleviated with analgesics. The transaminitis is self-limiting and typically resolves within 2 weeks.

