5.1.3.4 Duration of Prodrug Therapy

All subjects will receive a one week (7 day) course of 5-FC (Ancobon[®]) + vGCV (Valcyte[®]) prodrug therapy beginning two days after the adenovirus injection (**Figure 5**).

5.1.3.5 5-Fluorocytosine (5-FC, Ancobon[®]) Dose

The 5-FC (Ancobon[®]) dosage will be 150 mg/kg per day given in four equally divided doses. Due to 5-FC (Ancobon[®]) only being available in 250 and 500 mg capsules, the dose may be rounded up or down to the nearest possible amount. The capsules will be taken a few at a time over a 15 minute period.

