5.1.3.7 Toxicity

The most common side effects associated with 5-FC (Ancobon[®]) + vGCV (Valcyte[®]) prodrug therapy include neutropenia and thrombocytopenia. In five previous phase 1/2 trials representing 79 subjects (36-44), 19 of 79 (24%) subjects exhibited grade 1 - 3 neutropenia and 26 of 79 (33%) subjects exhibited grade 1/2 thrombocytopenia. The prodrugs may also contribute to anemia (32 of 79 subjects or 41%) and possibly lymphopenia (69 of 79 subjects or 87%). Except for lymphopenia, the vast majority of these events are mild (grade 1) to moderate (grade 2). Sixty-four percent (64%) of the events of lymphopenia were moderate (grade 2) and 25% were severe (grade 3). All hematologic events are transient and self-limiting, and typically resolve within two (anemia, neutropenia, thrombocytopenia) to six (lymphopenia) weeks.

Other possible side effects associated with 5-FC (Ancobon[®]) + vGCV (Valcyte[®]) prodrug therapy include nausea, vomiting, diarrhea and headache.

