6.2 Assessments Following the Study Therapy

Follow-up visits will occur at 1, 3, 6, 9, 12, 18 and 24 months after the adenovirus injection and then at least annually thereafter. Evaluations will include:

- 6.2.1** History and physical examination including DRE.
- 6.2.2** CBC/DP and blood chemistries.
- 6.2.3** Diagnostic serum PSA.
- 6.2.4** EPIC and EQ-5D instruments at 6, 12, and 24 months.
- 6.2.5** Ad5-*yCD/mutTK_{SR39}/rep*-hIL12 viral DNA in blood will be measured at every scheduled blood draw until not detected in two consecutive measurements.
- 6.2.6** Serum IL-12 and IFN- γ will be measured at every scheduled blood draw until not detected in two consecutive measurements.
- 6.2.7** A bone scan will be performed on any subject with complaints of bone pain that cannot be attributed to any intercurrent disease. Discretionary plain films and/or MRI may be needed to evaluate lesions seen on bone scan to confirm the diagnosis of metastatic disease.
- 6.2.8** In subjects with biochemical failure, a bone scan and CT scan of the abdomen and pelvis should be performed at that time and then annually and/or as clinically indicated.
- 6.2.9** Toxicity assessments will be performed at every scheduled follow-up visit using CRFs specifically designed for this trial. Toxicity assessments will be based on physical examinations, diagnostic evaluations, and laboratory test results.
- 6.2.10** It is understood that the performance of an individual study or test as specified in this protocol is subject to factors such as subject compliance, schedule difficulties, equipment malfunction, or the judgment of the principal investigator or patient care physicians, and that a test may not be done in an individual instance without violating the protocol. However, any systematic modification of the original protocol in this regard, whether related to subject safety or not, will be submitted to the IRB for approval.

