8.1.2 Secondary Endpoints

8.1.2.1 Hypothesis 1- Oncolytic adenovirus-mediated cytotoxic and IL-12 gene therapy has an effect on serum PSA levels.

Serum PSA will be assessed according to Table 7 and compared to the subject's baseline value.

8.1.2.2 Hypothesis 2- Oncolytic adenovirus-mediated cytotoxic and IL-12 gene therapy has an effect on PSADT.

Serum PSA will be assessed according to Table 7. PSADT will be determined by logarithm regression analysis as described previously (38). PSADT prior to the study therapy will be calculated using a minimum of three PSA values including the last PSA prior to initiation of the study therapy. Subjects who do not have at least three pre-treatment PSA values will be excluded from the analysis. PSADT after the study treatment will be calculated from the nadir and will use all PSA values prior to the implementation of additional salvage therapy such as ADT.

PSADT will be calculated assuming first-order kinetics using the following equation:

$$\ln(\text{PSA}) = \beta_0 + \beta_1 t$$

where β_0 is the point where the regression line crosses the ordinate at $t = 0$ and β_1 is the number of units that $\ln(\text{PSA})$ changes for every one-unit change in time (i.e., the slope). PSADT is defined as $\ln(2) / \beta_1$. Data are evaluated for normality the ranked data are considered if data are not normal.

8.1.2.3 Hypothesis 3- Oncolytic adenovirus-mediated cytotoxic and IL-12 gene therapy has no significant effect on quality of life.

We will use two instruments to measure QOL: EPIC and EQ-5D. QOL instruments will be collected on all subjects at baseline, 6, 12 and 24 months after the adenovirus injection.

EPIC questionnaires will be completed by the subject. The questionnaires will be summarized into three endpoints of function and bother in urinary, bowel and sexual domains with a score of 0 to 100. EQ-5D will have a self-report score of 1 to 3 in five domains (mobility, self-care, usual activity, pain/discomfort and anxiety/depression), and an overall health score 10 to 100. If a subject death is related to prostate cancer or the study treatment, the worst score will be given and the subject will be included in the analysis.

Data will be evaluated for normality, data transformation or nonparametric approach will be considered if data are not normal.

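### Quality of life is first re-measured at 6 months, so Hypothesis 3 can be tested only for late effects, although it is worded without that limit

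*Combined protocol and SAP*

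**What the plan says.** Section 8.1.2.3 states the hypothesis that the gene therapy "has no significant effect on quality of life" and fixes the schedule: "QOL instruments will be collected on all subjects at baseline, 6, 12 and 24 months after the adenovirus injection". Section 6.2.4 gives the same post-treatment times: "EPIC and EQ-5D instruments at 6, 12, and 24 months". Section 6.2 also schedules clinic visits at 1 and 3 months, with no questionnaire listed for them.

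Exposure is short: one injection on day 1, then prodrugs starting two days later. Section 5.1.3.4 reads: "All subjects will receive a one week (7 day) course of 5-FC" (given together with vGCV).

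Expected effects are described as brief. In section 5.1.2.8: "The flu-like symptoms typically resolve within a few days and can be alleviated with analgesics" and "The transaminitis is self-limiting and typically resolves within 2 weeks". In section 5.1.3.7: "All hematologic events are transient and self-limiting, and typically resolve within two (anemia, neutropenia, thrombocytopenia) to six (lymphopenia) weeks". Section 5.1.2.8 also lists infection, gross hematuria and urinary retention as risks of the injection, and a range of possible IL-12 effects for which it gives no duration.

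For PSA doubling time, section 8.1.2.2 uses post-treatment values only up to the start of further salvage therapy. The quality-of-life text has no matching rule. It does assign the worst score when a death is related to prostate cancer or to the study treatment.

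**The concern.** The hypothesis covers any effect on quality of life, but none of the assessments falls in the period when most treatment effects are expected. If men feel worse for days or weeks and then recover, the baseline and 6-month scores can look alike. A non-significant result could then be reported as no effect on quality of life, when the early period was never measured. This matters most for the transrectal intraprostatic injection, whose local effects are the kind EPIC is built to record, and for IL-12, which is new to this platform and which the protocol says may worsen flu-like symptoms.

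A second, smaller issue concerns the later scores. There is no control arm, so a change at 12 or 24 months may reflect the study therapy, disease progression or salvage treatment, and the plan does not say how scores after salvage therapy are to be handled.

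**Working it through.** The plan gives no margin, effect size or power for quality of life, so there is no figure to reproduce. The check is a timeline.

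**Inputs**
- Injection on day 1 (Figure 5).
- Prodrugs start on day 3 and run for 7 days (Figure 5, section 5.1.3.4), so the last day is 3 + 7 − 1 = day 9.
- Longest stated recovery: 6 weeks = 42 days, for lymphopenia (section 5.1.3.7). Transaminitis and the other hematologic events: 2 weeks = 14 days (sections 5.1.2.8 and 5.1.3.7).
- First repeat questionnaire: 6 months, taken as 182.6 days, so 1 + 182.6 = 183.6, about day 184.

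**Gap = day of first questionnaire − (start day + recovery time)**

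| Recovery counted from | Recovery | Resolved by | Gap to 6-month questionnaire |
|---|---|---|---|
| Injection (day 1) | 6 weeks | day 43 | 183.6 − 43 ≈ 141 days = 20.1 weeks |
| End of prodrugs (day 9) | 6 weeks | day 51 | 183.6 − 51 ≈ 133 days = 18.9 weeks |
| Injection (day 1) | 2 weeks | day 15 | 183.6 − 15 ≈ 169 days = 24.1 weeks |
| End of prodrugs (day 9) | 2 weeks | day 23 | 183.6 − 23 ≈ 161 days = 22.9 weeks |

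The six-week figure is the most generous one, and it belongs to a laboratory count. Flu-like symptoms, which a patient would notice, are said to last days, so for them the gap is wider.

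**Assessments inside the six-week period**
- As planned (6, 12, 24 months): 0 of 3. None falls inside the day-30 primary toxicity window either.
- With months 1 and 3 added: month 1 is 1 + 30.44 ≈ day 31, before day 43; month 3 is 1 + 91.3 ≈ day 92, after day 51. That gives 1 of 5 inside the period, and one further assessment to show recovery.

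**Table 7 against the text**
In the copy reviewed, the EPIC/EQ-5D row of Table 7 carries footnote i (every follow-up visit, which would include months 1 and 3). Footnote j (6, 12 and 24 months) is attached to no row. Sections 6.2.4 and 8.1.2.3 both give the times in footnote j. The likeliest explanation is a superscript j that was misread as i, but only the original document can settle it.

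**The case against.** Late measurement is defensible. Sections 1.1.1 to 1.1.4 describe the harms of other salvage options largely as incontinence, stricture or retention, bowel injury and erectile dysfunction, and a 6-to-24-month schedule can detect lasting change of that kind. A reader might infer that the schedule cannot answer Hypothesis 3 at all. That goes too far: it answers a long-term question.

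Acute harm is also not unobserved. Toxicity through day 30 is the primary endpoint, graded twice weekly at first and then at every visit. This stands, but clinician grading is not the patient-reported outcome that Hypothesis 3 names.

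The remedy has limits. By the protocol's own durations, most effects other than lymphopenia should be over by day 31. A month-1 score may miss effects lasting only days; the EQ-5D visual scale rates current health, and the documents give no recall period for EPIC. This stands, and it limits what a month-1 result can claim. The stated durations also come from vectors without IL-12, so the time course here is uncertain.

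Two further inferences are tempting but unsupported. One is that the timing pushes every result toward the null: it does so for early effects, but progression, salvage treatment and the worst-score rule can push late scores toward apparent harm. The other is that many men will be on salvage ADT by 12 to 24 months. The documents give no such proportion. Section 1.2.2.1.3 reports one Trial 1 subject starting ADT 2 months after gene therapy, and a projected mean delay of 2.2 years, which is not a rate.

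Finally, if footnote i in Table 7 is genuine, early questionnaires are already scheduled there, and the problem becomes a contradiction with sections 6.2.4 and 8.1.2.3.

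**Conclusion.** The point holds in a limited form. On the schedule given in sections 6.2.4 and 8.1.2.3, the first repeat measurement comes about 19 to 20 weeks after the latest stated resolution of expected toxicity. Early loss of quality of life that recovers cannot be seen, and a null result supports only a statement about 6 months and later. The hypothesis as worded is broader than that.

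This rests on the protocol's recovery times, which derive from earlier vectors and prodrugs. An IL-12 effect would be visible at 6 months only if it outlasted those times by about 19 weeks or more; the documents do not say whether any would.

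The handling of scores after salvage therapy is a genuine gap of unknown size. The priority is low: the endpoint is secondary, the trial is descriptive with 15 to 30 men, and neither the MTD definition nor the stopping rules use quality of life. The ANCOVA in section 8.1.2.3 also names a treatment variable that is undefined without a control arm, and better timing alone does not resolve that.

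**What to change.** 1. Add EPIC and EQ-5D at the existing 1- and 3-month visits, in section 6.2.4, Table 7 and section 8.1.2.3. Report the change at month 1 as early quality of life, stating that effects lasting only days may already have resolved, and use month 3 to describe recovery.
2. If these are not added, reword Hypothesis 3 to cover quality of life at 6 months and later only.
3. Report the later scores twice: with all data, and with scores after the start of salvage therapy excluded, in line with the PSA doubling-time rule. Give the number of men on salvage therapy at each visit. Men who remain in the second analysis are selected for not having needed salvage treatment, so neither analysis isolates the effect of the study therapy.
4. Check the footnote on the EPIC/EQ-5D row of Table 7 against the original and reconcile it with sections 6.2.4 and 8.1.2.3.

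Cost: two more questionnaire sets per subject, or 30 to 60 sets for 15 to 30 men, with the data entry and no new visits. Section 1.4.2 puts EQ-5D at about 5 minutes; no completion time is given for EPIC. The early scores cannot be recovered once a subject has passed those visits, so the decision is best made before enrollment.

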1.4.2 Utility as Measured by the EQ-5D

The EQ-5D is a two-part, self-assessment questionnaire that takes approximately 5 minutes to complete (66). The first part consists of 5 items covering 5 dimensions including: mobility, self care, usual activities, pain/discomfort, and anxiety/depression. Each dimension has an index score of 1- no problems, 2- moderate problems, or 3- extreme problems. The second part is a visual analogue scale (VAS) valuing current health state, measured on a 20-cm 10-point interval scale. Worst imaginable health state is scored as 0 at the bottom of the scale, and best imaginable health state is scored as 100 at the top. Both the 5-item index score and the VAS score are transformed into a utility score between 0 "Worst health state" and 1 "Best health state". The EQ-5D will be completed by the patient.

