For each QOL domain variable, analysis of variance and covariance (ANCOVA) will be used. Analysis will include the baseline covariates of pre-treatment domain score, covariate of time (of assessment post-treatment) and the independent

treatment variable. The analysis will start testing for treatment by time interaction, followed by testing the treatment effect at each time point if the interaction is detected at critical value 0.10, or testing the overall treatment effect or time effect at critical value of 0.05 if otherwise.

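### Section 8.1.2.3 starts the EQ-5D health score at 10 where section 1.4.2 starts it at 0, so a death given the worst score would get 10; separately, the 0–1 utility of 1.4.2 has no analysis

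*Combined protocol and SAP*

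**What the plan says.** Section 1.4.2 describes the instrument. Its first part has five items: "Each dimension has an index score of 1- no problems, 2- moderate problems, or 3- extreme problems". Its second part is a visual analogue scale (VAS), "measured on a 20-cm 10-point interval scale", with these anchors: "Worst imaginable health state is scored as 0 at the bottom of the scale, and best imaginable health state is scored as 100". It adds: "Both the 5-item index score and the VAS score are transformed into a utility score between 0" (worst) and 1 (best). It gives no formula or value set for that step.

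Section 8.1.2.3, the analysis text for quality of life, says "EQ-5D will have a self-report score of 1 to 3 in five domains" "and an overall health score 10 to 100". The next sentence assigns the worst score to any man whose death is attributed to the cancer or to study therapy, and keeps him in the analysis. It gives no number for any scale. The model follows: "For each QOL domain variable, analysis of variance and covariance (ANCOVA) will be used". No part of section 8 mentions a utility.

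EPIC, the other instrument, is scored 0 to 100 per domain in 8.1.2.3. Quality of life is measured at baseline, 6, 12 and 24 months.

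**The concern.** The two sections give different lower limits for one scale, and an analysis rule depends on that limit. An analyst who takes the range from 8.1.2.3 enters 10 for a qualifying death. One who takes the anchors from 1.4.2 enters 0. Under the first choice, a living man who records the bottom of the scale has a lower score than a man who died of his cancer or its treatment, which defeats the purpose of the imputation. A data check built on 10 to 100 (section 7.8 plans checks for miscoded and outlying fields) would also query a recorded 0, which 1.4.2 treats as valid.

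The second gap is that 1.4.2 leads the reader to expect a utility between 0 and 1, and section 8 gives it no analysis. Whether it is to be reported, and how it is to be derived, is left open until the data are in hand.

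**Working it through.** **Inputs**
- VAS limits in 1.4.2: 0 to 100.
- Overall health score limits in 8.1.2.3: 10 to 100.
- Item coding: 1 to 3, with 3 the worst, in 1.4.2; 1 to 3 in 8.1.2.3.
- Sample size: 15 to 30 (sections 3.1 and 8.2).
- Number of qualifying deaths, d: not given; an assumption, shown for 1 to 3.

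**Can the 10 be reproduced?** Not from the anchors in 1.4.2, which give 0. The ten-point description might be its source. If points lie 10 apart and the top is 100, a scale from 10 has (100 − 10)/10 + 1 = 10 points, and a scale from 0 has (100 − 0)/10 + 1 = 11. But 1.4.2 states no step size, and it places the worst state of that same scale at 0. The origin of the 10 is therefore conjecture, and the two ranges conflict.

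**Worst score under each reading**
- VAS, 1.4.2: 0.
- Overall health score, 8.1.2.3: 10.
- Each EQ-5D item, both sections: 3.
- Utility, 1.4.2: 0.

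**Effect on the mean.** The difference between the two floors is 10 − 0 = 10 points per death. If all N men contribute at an assessment, the raw mean differs by d × 10/N:
- N = 15: d = 1 gives 10/15 = 0.67; d = 2 gives 20/15 = 1.33; d = 3 gives 30/15 = 2.0.
- N = 30: d = 1 gives 10/30 = 0.33; d = 2 gives 20/30 = 0.67; d = 3 gives 30/30 = 1.0.

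With missing questionnaires N is smaller and the shift is larger in proportion.

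**Effect on a utility.** This depends on a transformation that the plan does not give. If the VAS is divided by 100, a floor of 10 becomes 10/100 = 0.10 and a floor of 0 becomes 0. If each scale is stretched over its own range, a floor of 10 becomes (10 − 10)/(100 − 10) = 0, and the difference disappears.

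**The case against.** The strongest reply is that this hardly matters. Section 1.4.2 is background, 8.1.2.3 never says that a death scores 10, and the only text that puts a number on the worst state says 0. A careful analyst would use 0. Few deaths will qualify: in the sponsor's earlier trial in this setting (section 1.2.2.1.3), 16 men had 7-year disease-specific survival of 94%, which is about one death (15/16 = 93.75%), and men lost to follow-up were counted as prostate cancer deaths. That trial used a different vector, so it is only a guide, but quality of life here stops at 24 months. Section 8.3 also calls the trial's analysis descriptive.

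Most of this stands, and it limits the severity. It does not remove the conflict. The range and the death rule are adjacent in the analysis section, so the natural reading is 10, and a descriptive mean still needs a defined range and death value.

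A reader might infer more than the documents support:
- **That two planned utility endpoints were replaced by six variables, raising the false-positive rate.** Objective 2.2.5 names only quality of life, and no section plans an analysis of two utilities. There is no such comparator, and a rate that treats items of one questionnaire as independent has no basis in the plan.
- **That the item coding differs.** It is 1 to 3 in both sections.
- **That ANCOVA is imposed on three-level items.** Section 8.1.2.3 allows a transformation or a nonparametric method when data are not normal.
- **That items running the opposite way to the VAS is an error.** Each variable is analysed separately. Direction matters only in that the death score must be stated for each scale.

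**Conclusion.** Wrong as written; minor. The lower limit of 10 in 8.1.2.3 contradicts the 0 in 1.4.2, and the rule for deaths relies on it. That a death scores 10 is the plain reading of 8.1.2.3 and not a number the plan states.

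The cost is 0.33 points (30 men) to 0.67 points (15 men) on the mean health score per imputed death. This assumes that every man contributes to the mean; the number of deaths is unknown. It affects a secondary endpoint and has no bearing on dose-limiting toxicity or the maximum tolerated dose.

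The missing utility analysis is a separate inconsistency. The documents do not show whether a utility was meant to be an outcome, so it cannot be called an omitted endpoint, only an unresolved one.

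**What to change.** 1. In 8.1.2.3, change the range of the overall health score to 0 to 100, to match 1.4.2, and set any database range check to the same limits.
2. State the worst score for a qualifying death on each scale: 0 on the VAS, 0 on each EPIC domain and 3 on each EQ-5D item. The protocol does not say which end of EPIC is worse. The 0 here assumes that higher is better, and the text should state the direction.
3. Reconcile 1.4.2 with 8.1.2.3 in one of two ways: name the utility as an analysed outcome and specify how the index and the VAS are transformed to it; or say that only the domain scores and the VAS are analysed, and mark the utility in 1.4.2 as a description of the instrument.

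Items 1 and 2, and the second option in item 3, are wording changes with no new data. The first option in item 3 costs slightly more, because a transformation must be chosen and cited before analysis.

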5.1.2.5 Ad5-yCD/mutTK_{SR39}rep-hIL12 Adenovirus Dose

The treatment schema is depicted in **Figure 5**.

Dosing of the Ad5-yCD/mutTK_{SR39}rep-hIL12 adenovirus is shown in **Table 5**. The starting dose level will be 1×10^{10} vp. The interval between dosing of the first two subjects in the first cohort should be ≥ 2 weeks.

All subjects in each cohort will be evaluated for ≥ 30 days before proceeding to the next cohort. If one of three subjects experiences a dose-limiting toxicity (DLT) (defined in Section **6.3.2.3**), three additional subjects will be enrolled at that dose level. If only one of six subjects experiences a DLT at a given dose level, the dose will escalate to the next cohort of three subjects. If two subjects experience a DLT at a given dose level, the maximum tolerated dose (MTD) is exceeded. Three

additional subjects will be enrolled at the previous dose level if there were only three subjects at that dose. The adenovirus dose will be escalated to a maximum of 1×10^{12} vp.

Table 5. Ad5-yCD/mutTK_{SR39}rep-hIL12 Dosing		
Cohort	# Subjects	Adenovirus Dose (vp)
1	3 to 6	1×10^{10}
2	3 to 6	3×10^{10}
3	3 to 6	1×10^{11}
4	3 to 6	3×10^{11}
5	3 to 6	1×10^{12}

Toxicity Assessments

[figure not shown]

Figure 5. Treatment Schema. Subjects will undergo a series of pre-treatment evaluations and must meet all of the eligibility criteria to be enrolled in the study. Subjects will receive a single intraprostatic injection of the Ad5-yCD/mutTK_{SR39}rep-hIL12 adenovirus at one of five dose levels (see Table 5) on day 1. Two days later (day 3), subjects will receive a one week (7 day) course of 5-FC (150 mg/kg/day) + vGCV (1,800 mg/day) prodrug therapy. Toxicity assessments will occur twice a week during the first two weeks and then at every scheduled follow-up visit. The primary endpoint is toxicity through day 30.

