8.3 Statistical Analysis

Analysis for this phase 1 trial will be descriptive. We will report all toxicity results taking into account any baseline abnormalities.

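### No test specified for quality of life can address Hypothesis 3: the planned treatment and treatment-by-time terms have no comparator in a single-arm trial

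*Combined protocol and SAP*

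**What the plan says.** Hypothesis 3 in section 8.1.2.3 is that "Oncolytic adenovirus-mediated cytotoxic and IL-12 gene therapy has no significant effect on quality of life". EPIC and EQ-5D are collected at baseline, 6, 12 and 24 months. Each domain score goes into an ANCOVA with the baseline score, time of assessment and a treatment variable whose levels are not defined. The sequence is: "The analysis will start testing for treatment by time interaction, followed by testing the treatment effect at each time point". That second step applies only when the first test is significant at 0.10; failing that, the plan tests either an overall effect of treatment or an effect of time, at 0.05. No equivalence margin or important difference is stated.

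On design, the Figure 5 legend in section 5.1.2.5 says "Subjects will receive a single intraprostatic injection of the" study adenovirus, at one of five dose levels. Section 5.1.3.4 gives the same seven-day prodrug course to everyone. Section 8.3 states: "Analysis for this phase 1 trial will be descriptive".

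On scoring, section 8.1.2.3 describes the EQ-5D as having "an overall health score 10 to 100". Section 1.4.2 says: "Worst imaginable health state is scored as 0 at the bottom of the scale". Section 8.1.2.3 assigns the worst score after a death related to prostate cancer or study treatment.

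**The concern.** The model reads as if written for a two-arm trial, and this trial has one arm. Secondary objective 2.2.5 therefore has a prespecified test sequence that does not match its hypothesis. Left as it stands, the replacement would have to be chosen once data are in hand. Because the hypothesis is one of no significant effect, with significance tests as the only stated criterion and no margin, a non-significant result in a small sample could be taken as reassurance.

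**Working it through.** **Sample size.** Table 5 gives five cohorts of 3 to 6 men: 5 × 3 = 15 and 5 × 6 = 30. This reproduces the 15 to 30 in sections 3.1 and 8.2. No QOL power, SD or margin is stated, so effects below are in SD of the change score and are assumptions, with all men observed.

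**Treatment as treated versus untreated.** The model has 7 columns: intercept, baseline, two visit indicators, treatment, and two treatment-by-visit products. With treatment equal to 1 for every man, the treatment column equals the intercept and each product equals its visit indicator. Three columns are redundant, so the rank is 7 − 3 = 4. The treatment effect and the interaction cannot be estimated.

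**Treatment as dose cohort.** Five groups give 16 columns of rank 16, so the model runs. It asks whether doses differ, not whether the therapy changes QOL. At one visit with one covariate, the F test has 4 and N − 6 degrees of freedom and noncentrality N·f², where f is an assumed effect size:

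| N | f = 0.25 | f = 0.40 |
|---|---|---|
| 15 | 8% power | 14% |
| 30 | 14% | 32% |

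**Time effect.** This is estimable. With baseline as a covariate, it contrasts 6, 12 and 24 months with each other. If every visit is 0.5 SD below baseline, each contrast is (−0.5) − (−0.5) = 0, so the loss goes into the intercept and is not tested.

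**A paired change-from-baseline test, if one were substituted.** Two-sided 5%, noncentrality d√n, d = 0.5:
- n = 15: 0.5 × √15 = 1.94, critical t (14 df) 2.145, power 44%, missed 56%.
- n = 30: 0.5 × √30 = 2.74, critical t (29 df) 2.045, power 75%, missed 25%.

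For d = 0.3, power is 19% and 36%; for d = 0.8, 82% and 99%. With 12 men observed, power at d = 0.5 is 35%.

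**Repeated visits.** The plan does not say how they are handled. Suppose rows were treated as independent.
- *Time test.* Assume equal correlation ρ among all four visits. The true variance of a visit contrast is proportional to 1 − ρ, while the model uses the residual variance after baseline, 1 − ρ². The ratio is 1/(1 + ρ): 0.67 at ρ = 0.5 and 0.59 at ρ = 0.7. The standard error is too large and the test is conservative. Simulation at n = 15 and n = 30 gives a type I error of about 1% to 2%.
- *Pooled mean change over three visits*, which the plan does not specify. With correlation ρ among the three change scores, the variance is understated by 1 + 2ρ, and the type I error is 2[1 − Φ(1.96/√(1 + 2ρ))]: 17% at ρ = 0.5 and 21% at ρ = 0.7.

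**Precision of an estimate.** The 95% half-width is t/√n: 2.145/√15 = 0.55 SD and 2.045/√30 = 0.37 SD.

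**The case against.** Several stronger readings are tempting, and the documents do not support them.

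- *That nothing can be run for objective 2.2.5.* The time effect can be fitted, and section 8.3 with the fixed instruments and visits allows descriptive summaries. What is missing is a specified test that bears on Hypothesis 3.
- *That treatment is certainly a constant.* The plan leaves it undefined. Dose cohort is a possible reading, given five dose levels and a primary objective about dose-dependent toxicity. It makes the model estimable, but answers another question with little power.
- *That the planned test has an inflated error rate.* The plan neither states nor excludes a within-subject term. If correlation were ignored, the surviving time test would be conservative. The 17% to 21% belongs only to a pooled test that the plan does not contain.
- *That the plan will declare no effect from a non-significant p-value.* It never says so. The 56% and 25% show the risk if that rule were adopted.
- *That the EQ-5D range matters much.* It affects one score, after certain deaths. Section 1.2.2.1.3 reports 94% disease-specific survival at 7 years in the sponsor's earlier locally recurrent trial, so the rule would seldom apply.

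It is also fair that QOL is a secondary objective of a dose-finding study and enters no escalation or stopping rule. That stands, and it limits the severity.

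**Conclusion.** The QOL analysis is wrong as written and should be fixed. Under each available reading, the specified tests are either inestimable (treated versus untreated), directed at dose differences (cohort), or blind to a uniform loss (time). None addresses "gene therapy has no significant effect on quality of life", and the test sequence conflicts with the descriptive statement in section 8.3. The estimability result follows from the design and needs no assumed figure. The missed-loss figures of 56% and 25% assume a true 0.5 SD change, complete data on 15 or 30 men, and a two-sided 5% paired test that the plan does not name. Early stopping of escalation or missing 24-month forms would make them worse. The MTD objective is unaffected. The EQ-5D range is a minor inconsistency.

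**What to change.** Replace the ANCOVA paragraph in section 8.1.2.3 with estimated mean change from baseline for each domain at 6, 12 and 24 months with 95% confidence intervals. Either separate per-visit estimates or a repeated-measures model will do; the model should have visit as a factor, a centred baseline covariate and a within-subject covariance. Show results by dose level descriptively. Reword Hypothesis 3 as estimation, and claim no material worsening only where the interval excludes a difference stated in advance. Reconcile the paragraph with section 8.3. Use one range for the EQ-5D overall score in sections 1.4.2 and 8.1.2.3, so that the worst score is defined.

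The cost is wording only: no added subjects, visits or data. The downside is that a claim of no effect becomes harder to make. The expected half-width is about 0.55 SD at n = 15 and 0.37 SD at n = 30. By symmetry with the power calculation, if the true change were zero, the 95% interval would exclude a 0.5 SD loss only 44% of the time with 15 men and 75% with 30.
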